### **11.5 Accrual**

The rate of accrual for the study is expected to be about 4 patients per month. It is estimated 67 eligible patients will be enrolled in 12 months.

### **11.6 Continuous Toxicity Monitoring using Pocock-type boundary**

The toxicities will be reviewed and monitored on a continuous basis. Early stopping of this trial will be based on the excessive Lattice SBRT treatment emergent severe adverse events (TSAE) of grade 3 or higher non-hematological rate. We assume the TSAE rate is expected ~30% or less and a toxicity rate of 40% or more is not desired. Sequential boundaries will be used to monitor dose-limiting toxicity rate after three patients are enrolled and evaluable for toxicity. The accrual will be halted if excessive numbers of TSAE are seen, that is, if the number of TSAE is equal to or exceeds  $b_n$  out of  $n$  patients with full follow-up (see table below). This is a Pocock-type stopping boundary that yields the probability of crossing the boundary at most 0.3 when the rate of TSAE is equal to the acceptable rate of 0.3 (Ivanova, Qaqish, and Schell 2005).

number of patients	3	4	5	6	7	8	9	10	11	12	13	14	15	16	17	18	19	20	21	22
Boundary (bn)	3	3	4	4	5	5	6	6	7	7	7	8	9	9	9	9	9	10	10	
number of patients	23	24	25	26	27	28	29	30	31	32	33	34	35	36	37	38	39	40	41	42
Boundary (bn)	10	11	11	11	12	12	12	13	13	13	14	14	14	15	15	15	16	16	17	17
number of patients	43	44	45	46	47	48	49	50	51	52	53	54	55	56	57	58	59	60	61	62
Boundary (bn)	17	18	18	18	19	19	19	20	20	20	21	21	21	22	22	22	23	23	23	24
number of patients	63	64	65	66	67															
Boundary (bn)	24	24	25	25	25															

Thus, based on the continuous monitoring algorithm for toxicity using Pocock-type boundary, the study will halt if excessive Lattice SBRT -related adverse events occur in the 3 of the first 3 patients, or 4 of the first 6, or 5 of the first 9, or 5 of the 10 patients has completed the trial.

The operating characteristics including early stopping probability, expected number of TSAsEs and associated with the calculated boundaries are listed below.

TEAE rate	Early stopping (hitting the boundary) probability	Expected number of TEAEs	Standard deviation on number of TEAEs	Expected number of patients enrolled	Standard deviation of number of patients enrolled	Expected TEAE rate	Standard deviation on TEAE rate
0.30	0.3980	14.08	6.93	46.94	26.85	0.41	0.23
0.40	0.8648	9.76	7.27	24.38	22.99	0.56	0.22
0.50	0.9950	5.63	4.22	11.26	11.69	0.66	0.22
0.60	1.0000	3.85	2.24	6.41	5.76	0.75	0.21
0.70	1.0000	3.03	1.36	4.32	3.28	0.82	0.19
0.80	1.0000	2.56	0.88	3.20	1.98	0.89	0.15
0.90	1.0000	2.24	0.53	2.49	1.11	0.95	0.11
1.00	1.0000	2.00	0.00	2.00	0.00	1.00	0.00

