## 1.7 Risk/Benefit Assessment

### 1.7.1 Known Potential Risks

High-dose radiation has been known to cause toxicity to normal tissue. This is manifested variably depending on the area of the body treated. While the potential toxicities can be serious and include death, these toxicities are rare when high-quality, high-dose radiation is delivered within established normal tissue dose constraints using appropriate immobilization, image guidance, and institutional experience.

We have successfully tested Lattice SBRT plans prescribed to 66.7 Gy in 5 fractions using institutional quality assurance protocols similar to conventional SBRT and have implemented this treatment approach in the LITE SABR M1 pilot study with few treatment related toxicities. At the time of this writing, LITE SABR M1 has accrued 15 patients. A review of the first 8 patients and a data safety monitoring report was completed on 4/29/2020. This passed review and found no protocol SAEs. Since that time, we have had one potentially treatment-related grade 3+ toxicity.

Given this experience, we continue to expect that the toxicity risks associated with Lattice SBRT plans to be similar or better than conventional SBRT for large tumors if the required established dose constraints are met. Blood collection prior to and after radiotherapy poses a small risk of pain and bleeding.

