## **10.0 DATA AND SAFETY MONITORING**

In compliance with the Washington University Institutional Data and Safety Monitoring Plan, the Principal Investigator will provide a Data and Safety Monitoring (DSM) report to the Washington University Quality Assurance and Safety Monitoring Committee (QASMC) semi-annually beginning six months after accrual has opened (if at least one patient has been enrolled) or one year after accrual has opened (if no patients have been enrolled at the six-month mark).

The Principal Investigator will review all patient data at least every six months, and provide a semi-annual report to the QASMC. This report will include:

- HRPO protocol number, protocol title, Principal Investigator name, data coordinator name, regulatory coordinator name, and statistician
- Date of initial HRPO approval, date of most recent consent HRPO approval/revision, date of HRPO expiration, date of most recent QA audit, study status, and phase of study
- History of study including summary of substantive amendments; summary of accrual suspensions including start/stop dates and reason; and summary of protocol exceptions, error, or breach of confidentiality including start/stop dates and reason
- Study-wide target accrual
- Protocol activation date
- Average rate of accrual observed in year 1, year 2, and subsequent years
- Expected accrual end date
- Objectives of protocol with supporting data and list the number of participants who have met each objective
- Measures of efficacy (phase I studies only if efficacy is objective of the protocol)
- Measures of efficacy
- Early stopping rules with supporting data and list the number of participants who have met the early stopping rules
- Summary of toxicities
- Abstract submissions/publications
- Summary of any recent literature that may affect the safety or ethics of the study

The study principal investigator and Research Patient Coordinator will monitor for serious toxicities on an ongoing basis. Once the principal investigator or Research Patient Coordinator becomes aware of an adverse event, the AE will be reported to the HRPO and QASMC according to institutional guidelines.

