## APPENDIX C: Reporting Timelines

Expedited Reporting Timelines		
Event	HRPO	QASMC
Serious AND unexpected suspected adverse reaction		
Unexpected fatal or life-threatening suspected adverse reaction		
Unanticipated problem involving risk to participants or others	Report within 10 working days. If the event results in the death of a participant enrolled at WU/BJH/SLCH, report within 1 working day.	Report via email after IRB acknowledgment
Major deviation	Report within 10 working days. If the event results in the death of a participant enrolled at WU/BJH/SLCH, report within 1 working day.	
A series of minor deviations that are being reported as a continuing noncompliance	Report within 10 working days.	
Protocol exception	Approval must be obtained prior to implementing the change	
Clinically important increase in the rate of a serious suspected adverse reaction of that list in the protocol or IB		
Complaints	If the complaint reveals an unanticipated problem involving risks to participants or others OR noncompliance, report within 10 working days. If the event results in the death of a participant enrolled at WU/BJH/SLCH, report within 1 working day. Otherwise, report at the time of continuing review.	
Breach of confidentiality	Within 10 working days.	
Incarceration	If withdrawing the participant poses a safety issue, report within 10 working days.  If withdrawing the participant does not represent a safety issue and the patient will be withdrawn, report at continuing review.	

Routine Reporting Timelines		
Event	HRPO	QASMC
Adverse event or SAE that does not require expedited reporting	If they do not meet the definition of an unanticipated problem involving risks to participants or others, report summary information at the time of continuing review	Adverse events will be reported in the toxicity table in the DSM report

Routine Reporting Timelines		
Event	HRPO	QASMC
		which is typically due every 6 months.
Minor deviation	Report summary information at the time of continuing review.	
Complaints	If the complaint reveals an unanticipated problem involving risks to participants or others OR noncompliance, report within 10 working days. If the event results in the death of a participant enrolled at WU/BJH/SLCH, report within 1 working day. Otherwise, report at the time of continuing review.	

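### Section 11.6 counts a treatment-related death as one grade 3+ event against limits set for a 30% rate, and the document states no death-specific threshold or pause

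*Combined protocol and SAP*

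**What the plan says.** **The rule.** Section 11.6 halts accrual on "excessive Lattice SBRT treatment emergent severe adverse events (TSAE) of grade 3 or higher non-hematological rate", that is, "if the number of TSAE is equal to or exceeds" the limit printed for the number of patients with full follow-up. It gives grades 4 and 5 no separate limit or weight. Section 9.1 records a fatal adverse event as grade 5 of that event, so it enters the count as one.

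**Its calibration.** "We assume the TSAE rate is expected ~30% or less and a toxicity rate of 40% or more is not desired". The boundary is said to be one that "yields the probability of crossing the boundary at most 0.3 when the rate of TSAE is equal to the acceptable rate of 0.3". On the first look: "Sequential boundaries will be used to monitor dose-limiting toxicity rate after three patients are enrolled and evaluable for toxicity".

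**What is said about fatal harm.** Section 1.7.1: "While the potential toxicities can be serious and include death, these toxicities are rare", on condition that high-quality treatment is delivered within normal-tissue limits. No fatality rate is given.

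**Other oversight.**
- Section 10: "The Principal Investigator will review all patient data at least every six months, and provide a semi-annual report to the QASMC". It adds that the investigator and coordinator monitor serious toxicity on an ongoing basis, and that adverse events they learn of go to the Human Research Protection Office (HRPO) and QASMC under institutional guidelines.
- Appendix C, for an unanticipated problem: "If the event results in the death of a participant enrolled at WU/BJH/SLCH, report within 1 working day". This is the HRPO column. QASMC is told after IRB acknowledgment (within 10 days of it, section 7.1.2). Events that need no expedited report reach QASMC in the semi-annual toxicity table.
- Section 5.11 lists closure of the study by the cancer center, without a criterion.

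**The concern.** A boundary tuned to separate 30% from 40% has little ability to detect a harm expected to be rare. If fatal toxicity ran well above rare while other severe toxicity stayed low, the pooled count could remain under its limits through several related deaths. The trial is single-arm, palliative and dose-escalated, so there is no control group against which an excess of deaths would stand out. What happens to accrual after a related death would then rest on judgement or on institutional policy. The document itself does not settle it.

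**Working it through.** **Inputs.** From section 11.6: the printed limits, from 3 at n=3 to 25 at n=67, with looks after each patient from n=3. Maximum n = 67 (section 11.1). The first row of limits shows 19 values for 20 sample sizes. This may be an extraction fault, so it is not counted as an error and two alignments are carried:
- Alignment A: the 19 values belong to n=3 to 21.
- Alignment B: they belong to n=4 to 22, with 3 at n=3.

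The 10% death rate is an assumption, varied below.

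**Method.** Let f(n,k) be the probability of k events in n patients without a halt. Then f(n,k) = (1-p)·f(n-1,k) + p·f(n-1,k-1). At each look, probability with k at or above the limit is moved to halted. The sum of the halted probability over n is the chance of ever halting. Patients are taken as independent.

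**The plan's own figures first.** Section 11.6 states a crossing probability of 0.3980 at a rate of 0.30 and 0.8648 at 0.40. The printed limits give 0.340 and 0.848 (A) or 0.388 and 0.862 (B), so the 0.3980 is not reproduced exactly. The same table shows 2.00 patients expected at a rate of 1.00, which is impossible if the first possible halt is at n=3. A constant-tail boundary (pointwise tail about 0.137 at rate 0.30) with a limit of 2 at n=2 gives 0.3981, 0.8647 and 2.00. The operating characteristics therefore appear to belong to a boundary with an extra look at n=2. They also exceed the stated maximum of 0.3.

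**Deaths as the only counted events.** Expected deaths are 67 × p, if all 67 are treated.

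| Death rate p | Chance of ever halting (A, B) | 67 × p |
|---|---|---|
| 5% | 0.05%, 0.12% | 3.4 |
| 10% | 0.44%, 0.96% | 6.7 |
| 15% | 1.7%, 3.3% | 10.1 |
| 20% | 5.1%, 8.3% | 13.4 |

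Hand check at 10%. Under A the limit is 3 at both n=3 and n=4, so the chance of halting by the fourth patient is P(at least 3 of 4) = 4 × 0.1³ × 0.9 + 0.1⁴ = 0.0037. Under B the limit is still 3 at n=5, and P(at least 3 of 5) = 10 × 0.1³ × 0.9² + 5 × 0.1⁴ × 0.9 + 0.1⁵ = 0.0086. Nearly all of the halting chance comes from an early cluster, and the remaining looks add about 0.001 or less.

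**Sensitivity at 10%.**
- Using the worked text's 5 of 9 and 5 of 10 in place of the table's values (alignment A): 0.52%.
- Adding a look at n=2 with limit 2: 1.2% (A) or 1.7% (B), of which 0.1² = 1.0% is two events in the first two patients.
- Using the boundary that matches the operating characteristics: 1.4%.

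**Adding non-fatal events.** The rule sees only the total grade 3+ rate. With 10% deaths inside that total:

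| Total grade 3+ rate | Chance of ever halting (A, B) |
|---|---|
| 15% | 1.7%, 3.3% |
| 20% | 5.1%, 8.3% |
| 25% | 14.4%, 19.0% |
| 30% | 34.0%, 38.8% |

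Under A the chance stays below 1% only while the total is about 12.5% or less (0.90% at 12.5%, 1.03% at 13%).

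**Early counts.** Two related deaths in the first 3 or 4 patients do not halt accrual, because the limit is 3. At n=10 the table's limit of 6 lets five pass; the worked text's limit of 5 lets four pass.

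**The case against.** Pooling is not an error. It matches the grade 3+ co-primary endpoint, and the recursion shows the rule working as a monitor of the overall severe-toxicity rate. The 5-20% death rates are scenarios with no source in the documents. Section 1.7.1 reports no protocol SAEs at the pilot's first 8-patient review, and one potentially related grade 3+ event after that. All of this stands, and it limits the point to a gap in the plan's safeguards.

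A reader might infer three stronger things that the documents do not support:

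1. That a treatment fatal to 10% of patients would trip the rule less than 1% of the time, whatever else it causes. The rule counts every non-hematologic grade 3+ event, and section 11.2 quotes 5-25% for grade 3+ toxicity in earlier studies. The sub-1% figure needs deaths to be essentially the only such events, and no look at n=2.
2. That QASMC learns of an anticipated related death only through the semi-annual report. Appendix C points that way for non-expedited events, but section 10 also sends adverse events to HRPO and QASMC under institutional guidelines. The two routes need reconciling; neither can be taken as the sole one.
3. That nothing anywhere would pause accrual. Sections 7.1.1 and 10 defer to the IRB policies and the institutional monitoring plan, which are not available here, and the cancer center may close the study. The supportable statement is that this document states no death-specific pause.

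**Conclusion.** The point holds in this limited form. Section 11.6 contains the document's only stated accrual halt. It gives a related death the weight of a grade 3 event, against limits designed for a 30% rate. At an illustrative 10% death rate with no other grade 3+ events, accrual would be halted about 0.4-1% of the time, or 1.2-1.7% with a look at n=2. At a total rate of 20%, the edge of the below-20% safety criterion in section 11.2, half the events could be fatal and the boundary would still go uncrossed about 92-95% of the time (100% minus 8.3% or 5.1%).

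These figures assume independent patients, a constant rate, and an outcome known at each look. Section 11.6 counts patients with full follow-up, so real looks would lag enrolment. The size depends heavily on the non-fatal rate. The absence of a stated death-specific threshold or pause does not depend on it.

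**What to change.** Keep the pooled boundary for the overall severe-toxicity rate. Add to section 11.6 a statement of how a grade 5 event judged related to treatment affects accrual, and when the existing QASMC reviews it. The statement should make clear that deaths from disease progression are excluded, since section 9.1 also records those as grade 5. The sponsor and QASMC should set the exact trigger; none is proposed here.

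In the same amendment, reconcile section 11.6 with:
- the description of fatal toxicity as rare in section 1.7.1;
- the reporting routes in section 10 and Appendix C;
- the below-20% safety criterion in section 11.2, against the 30% acceptable rate;
- its own figures: at most 0.3 against 0.3980, the table's limit of 6 at n=10 against 5 of 10 in the worked text, and whether there is a look at n=2.

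The cost is a short amendment using the existing committee and the existing Toxicity and Death Forms, with no added patients or procedures. If the chosen response includes a pause, accrual may occasionally stop briefly for a death later judged unrelated.

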### 11.2 Study Endpoints

The co-primary endpoints are rate of local control of the treated (i.e. target) lesion at 6 months, and proportion of patients with treatment related grade 3+ CTCAE v5.0 toxicity. Local control will be determined by RECIST 1.1 analysis of baseline compared with imaging at 6 months. Imaging may include CT scan, PET/CT, or MRI. It is strongly suggested that the same imaging modality is used between baseline and at every follow-up timepoint for staging of disease.

Importantly, there are limited available data to determine expected local control of large tumors after SBRT. Almost all studies have focused on tumors with average maximal diameter of only 5.5 cm corresponding to a tumor volume of approximately 87 cc. In such studies, local control rates are approximately 70-85%. In the pilot study of Lattice SBRT at Washington University, the median treated tumor volume was 435 cc (N=14). Likewise, these few studies of SBRT for large tumors report a grade 3+ toxicity rate of 5-25%, varying based on tumor location.

Due to the lack of a reliable historical comparison, the enrollment target was defined by clinical considerations as opposed to power calculations for comparison with a historical control. This study instead seeks to establish the expected local control rate at 6 months for patients with such large tumors treated with Lattice SBRT. After discussing with internal and external stakeholders, we determined that a clinically reasonable bound on local control at 6 months would be 15%. Approximately 47 patients would be required to determine local control with a 95% confidence interval of +/- 15%; 67 patients will be enrolled to get 47 evaluable patients. We anticipate that up to 30% of patients may not be evaluable for local control at 6 months and are accounting for this potential drop-out rate by enrolling 67 patients. This is because patients with very large tumors needing palliative radiotherapy often have short survival.

Likewise, the study seeks to establish the expected grade 3+ treatment related toxicity rate for treatment of large tumors with lattice SBRT. The treatment will be considered safe if the grade 3+ treatment related toxicity rate is less than 20%, which is in line with prior studies of SBRT of large tumors.

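### The toxicity monitoring in 11.6 treats a 30% severe-toxicity rate as acceptable, while the safety verdict in 11.2 requires a rate below 20%, and the two sections describe the event differently

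*Combined protocol and SAP*

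**What the plan says.** Section 11.2 (Study Endpoints) gives the rule for the co-primary safety endpoint: "The treatment will be considered safe if the grade 3+ treatment related toxicity rate is less than 20" per cent. It calls this consistent with earlier work, of which it says that "these few studies of SBRT for large tumors report a grade 3+ toxicity rate of 5-25%, varying based on tumor location". Section 1.7.1 expects toxicity to be "similar or better than conventional SBRT for large tumors if the required established dose constraints are met".

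Section 11.6 (Continuous Toxicity Monitoring) starts elsewhere: "We assume the TSAE rate is expected ~30% or less and a toxicity rate of 40% or more is not desired". Accrual halts "if the number of TSAE is equal to or exceeds" the tabulated limit among patients with full follow-up. The construction is said to be one that "yields the probability of crossing the boundary at most 0.3 when the rate of TSAE is equal to the acceptable rate of 0.3". For 63 to 67 patients the table reads "Boundary (bn) 24 24 25 25 25".

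The event is not worded consistently. Section 11.6 first names treatment-emergent, non-hematological events of grade 3 or higher, and later speaks of adverse events related to Lattice SBRT. Section 11.2 counts treatment-related grade 3+ toxicity, and the table in section 2.0 restricts this to non-hematologic events. Under section 5.8 every patient who received at least one fraction is evaluable for toxicity, so the denominator can reach 67.

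**The concern.** The verdict and the monitoring rule appear to concern the same harm from the same treatment. One says the treatment is not safe from 20% upward. The other labels 30% acceptable and objects only from 40%. The 30% lies above the safety limit and above the whole range that 11.2 cites.

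Two things are at stake. The monitoring gives little protection at true rates of about 20-30%, where the verdict is in doubt or likely to fail. And the report could be ambiguous: a trial with 24 of 67 patients affected (35.8%) could be described as never having crossed its boundary, while failing its own safety criterion.

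**Working it through.** **Inputs.** N = 67 (11.2, 11.4); verdict threshold below 20% (11.2); acceptable rate 0.30 and the printed limits b_n (11.6); toxicity denominator all treated patients (5.8). Assumptions: both rules count patients with treatment-related grade 3+ toxicity; the verdict uses the point estimate, since 11.2 names no estimator; outcomes are known at once, except in step 5.

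**1. The plan's own figure.** The exact recursion is P_n(k) = P_{n-1}(k)(1-p) + P_{n-1}(k-1)p, with a path stopped once k ≥ b_n. For a Pocock-type limit, take b_n as the smallest r with P(X ≥ r | n, 0.30) ≤ a constant. A constant of 0.137, with looks from the first patients, matches every printed limit from n = 23 to 67. It gives:
- at a true 0.30, stopping probability 0.3981 and expected enrolment 46.93; the plan prints "0.30 0.3980 14.08 6.93 46.94", that is 0.3980 and 46.94
- at a true 0.40, stopping probability 0.8647; the plan prints 0.8648

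So the limits are calibrated to 0.30, not 0.20. The printed 0.3980 also exceeds the ceiling of 0.3 stated in the same section.

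**2. Where the verdict is lost.** 0.20 × 67 = 13.4. So 13/67 = 19.4% passes and 14/67 = 20.9% fails.

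**3. Where the rule halts.** The smallest b_n/n over all looks is 25/67 = 37.3%; the next smallest are 24/64 = 37.5% and 23/61 = 37.7%. Earlier looks need a higher fraction, for example 3 of 3 or 4 of 6. The limit is 14 at n = 33 to 35 and 15 at n = 36, so 14 affected patients among 36 do not halt accrual and up to 67 - 36 = 31 more could be enrolled.

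**4. Operating characteristics of the printed limits.** The first row of the table, as it can be read, has 20 patient counts and 19 limits. The ranges cover every placement of the missing value that keeps the row non-decreasing.

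| True rate | Halt | Verdict fails, P(X ≥ 14 of 67) | No halt and verdict fails |
|---|---|---|---|
| 20% | 5-8% | 48% | 41-43% |
| 25% | 14-19% | 82% | 64-68% |
| 30% | 34-39% | 96% | 58-63% |

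**5. Patients treated after the 14th affected patient, in trials that never halt.** With outcomes known at once, the mean is 13.4 at a true 25% and 17.0 at 30%. The endpoint, however, runs to 6 months and accrual is about 4 per month (11.5), so about 6 × 4 = 24 patients enter during one window. If event times are assumed uniform over 6 months, the means fall to about 4 and 7, and nobody remains to be treated in about 45% and 26% of such trials. If status is known only at 6 months, the mean is below 1.

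**6. Is a looser limit in itself a fault?** The same construction with an acceptable rate of 0.20 and looks from n = 3 ends at 19 of 67 (total crossing probability at most 0.30) or 21 of 67 (at most 0.10). Both exceed 14.

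**The case against.** The strongest defence is that a halting boundary and a final criterion do different jobs. Step 6 bears this out: even limits built on 20% let a trial run past 14 affected patients. Sections 11.2 and 11.4 also describe an estimation study that needs 47 patients evaluable for local control, and nothing in the plan makes loss of the safe label a reason to stop. A reader might infer that enrolment after the 14th affected patient is pointless, or that the 14-against-25 gap is itself the error. The documents support neither.

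Three other strong readings also fail. The rule does not act only at 25 of 67; it can halt from the third patient. Nor is every true rate from 20% to 35% failed by the verdict and tolerated by the monitoring: at 20% the verdict passes about half the time (1 - 0.476 = 0.524), and at 35% the printed limits halt about 62-65% of trials. And 13 to 17 further patients is an upper case that depends on immediate outcomes.

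The event wording may explain part of the gap. An all-cause count would run higher in these patients and could justify a higher tolerated rate. But 11.6 also says the events are related to Lattice SBRT, so this defence itself needs a correction to the text. Finally, section 10.0 provides ongoing toxicity monitoring by the investigator and semi-annual reports to the QASMC. Review between 20% and 37% is therefore not absent, though no numerical trigger is given there.

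What stands is the design parameter: the plan labels 30% acceptable in one section and not safe in another, without explanation.

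**Conclusion.** The point holds as an unreconciled conflict between 11.2 and 11.6 in both tolerable rate and event definition. On the related-event reading, no look halts at an observed rate below 37.3%, and at true rates of 25-30% more than half of trials would complete without a halt and with a failed verdict.

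The probabilities rest on the point-estimate reading of the 20% criterion and on immediate outcomes. A confidence-bound reading would lose the verdict sooner: the exact 95% upper limit for 7 of 67 is already 20.3%. Because 11.6 counts patients with full follow-up, actual halts would come later than modelled. The conflict itself is certain; the number of extra patients exposed is not, and should be quoted only as a range that depends on event timing. The change should be made, because a co-primary conclusion relies on this threshold.

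**What to change.** Reconcile 11.2 and 11.6:

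- State one event definition for both sections: related or all-cause, non-hematologic or not, and over what window.
- State one tolerable rate, chosen by the sponsor, or explain why monitoring tolerates a higher rate than the verdict.
- Name the estimator behind the 20% criterion.
- Regenerate and reprint the limits and operating characteristics for the chosen rate, add rows for true rates of 0.20 and 0.25, and make the stated crossing probability agree with the table.
- If a QASMC review trigger is added, count patients with at least one qualifying event, not events, because the endpoint is a proportion of patients. A trigger at 14 affected patients would fire in about 12% of trials at a true 15% and 0.6% at 10%.

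The drafting cost is an amendment and one run of the boundary program. The statistical cost depends on the choice. If the sponsor keeps 20% and the 0.3 crossing level, the limits end at 19 of 67 and halt about 30% of trials at a true 20% and 10% at 15%. With a 0.10 crossing level they end at 21 of 67 and halt about 10% and 2%. The price is less protection at a true 30%: halting there is 63%, against 85% with the 0.3 level. This trade-off should be stated with the new table.

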## **5.8 Definitions of Evaluability**

All patients enrolled on the study are evaluable for toxicity if they have received at least one fraction of radiation. Patients are evaluated from first receiving study treatment until 90 days after the conclusion of treatment or death. Participants who are consented but do not receive study treatment will be replaced.

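### Section 11.6 describes its toxicity stopping rule in ways that cannot all be true: at most 0.3 in the text, 0.3980 in the operating-characteristics table, about 0.34 to 0.39 from the printed limits, and a 5-of-10 halt those limits do not contain

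*Combined protocol and SAP*

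**What the plan says.** All of these statements stand in Section 11.6 of the protocol unless noted.

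- **Design rates.** "We assume the TSAE rate is expected ~30% or less and a toxicity rate of 40% or more is not desired".
- **Rule.** Accrual halts "if the number of TSAE is equal to or exceeds" the limit b_n among n "patients with full follow-up (see table below"). Section 5.8 governs who counts for toxicity: "All patients enrolled on the study are evaluable for toxicity if they have received at least one fraction of radiation".
- **First look.** "Sequential boundaries will be used to monitor dose-limiting toxicity rate after three patients are enrolled and evaluable for toxicity".
- **Promised property.** The boundary "yields the probability of crossing the boundary at most 0.3 when the rate of TSAE is equal to the acceptable rate of 0.3".
- **Limits table.** Values for n = 3 to 67. The first row (n = 3 to 22) shows 19 values under 20 column heads; the other rows are complete.
- **Narrative examples.** "the study will halt if excessive Lattice SBRT -related adverse events occur in the 3 of the first 3 patients", at 4 of 6, at 5 of 9, or when "5 of the 10 patients has completed the trial".
- **Operating-characteristics table.** Stopping probability 0.3980 at a 30% rate and 0.8648 at 40%. Expected patients are 3.20, 2.49 and 2.00 at rates of 80%, 90% and 100%; expected events are 2.56, 2.24 and 2.00.

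**The concern.** The section gives four accounts of one rule: a promised probability, a table of limits, a table of operating characteristics, and worked examples. If all came from one boundary they would agree. The first and third disagree on sight (0.3 against 0.3980), and a ceiling expressed as 'at most' leaves no room for rounding. The third is also incompatible with a first look at three patients, and the fourth has a limit at n=10 that the second lacks.

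This is the trial's only quantitative early-stopping rule, and Section 10.0 requires semi-annual reports on the stopping rules with supporting data. A committee that sees 5 events in 10 patients, with no earlier limit reached, would find a sentence saying halt and a table saying continue. Anyone judging whether the rule is too strict or too lax would be relying on a false-stop probability that the printed limits do not have.

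**Working it through.** **Inputs (Section 11.6 unless noted)**

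- Stop when cumulative events reach b_n or more; first look at n = 3; maximum 67 patients (Section 11.1). All treated patients count (Section 5.8).
- First row as printed: 3, 3, 4, 4, 5, 5, 6, 6, 7, 7, 7, 8, 9, 9, 9, 9, 9, 10, 10, plus one missing value. The gap may come from text extraction and is not treated as an error. I placed it at each of the 20 positions with every value that keeps the row in ascending order and b_3 = 3, as the 3-of-3 example requires. That makes 27 fills and 8 distinct boundaries. In all of them b_6 = 4 and b_10 = 6.

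**Method.** Let f_n(k) be the probability of having k events after n patients without having stopped, with f_0(0) = 1 and event rate p.

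- Before the look: g_n(k) = (1 − p) f_{n−1}(k) + p f_{n−1}(k − 1).
- Probability of stopping at n: s_n = sum of g_n(k) over k ≥ b_n. For k < b_n, f_n(k) = g_n(k).
- Crossing probability = Σ s_n. Expected patients = Σ n·s_n + 67(1 − Σ s_n). Expected events = p × expected patients.

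**Step 1. Reproduce the operating-characteristics table.** No version of the printed limits gives 0.3980. A different boundary comes very close: limits set at a constant pointwise binomial tail of about 0.137 under p = 0.3, with an added stop at 2 of 2. It gives 0.3981 and 46.93 expected patients at 30% (table 0.3980 and 46.94), 0.8647 at 40% (table 0.8648), and 2.00 patients at 100% (table 2.00). It equals the printed limits for n = 23 to 67 but differs at several n between 7 and 20. This suggests, without proving it, that the table was computed for another rule.

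**Step 2. Compare the printed limits with the table**

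| Event rate | Stopping probability: table | Printed limits | Expected patients: table | Printed limits |
|---|---|---|---|---|
| 0.30 | 0.3980 | 0.340–0.388 | 46.94 | 47.8–51.6 |
| 0.40 | 0.8648 | 0.848–0.862 | 24.38 | 25.3–28.6 |
| 0.80 | 1.0000 | 1.0000 | 3.20 | 3.88–4.17 |
| 0.90 | 1.0000 | 1.0000 | 2.49 | 3.35–3.41 |
| 1.00 | 1.0000 | 1.0000 | 2.00 | 3.00 |

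Expected events under the printed limits are 3.10–3.33, 3.01–3.07 and 3.00 at 80%, 90% and 100%, against 2.56, 2.24 and 2.00 in the table. The impossibility needs no recursion: with a first look at 3 patients and a limit of 3, no stopped trial can have fewer than 3 patients or 3 events, and the table says every trial stops at these rates.

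**Step 3. The limit at n = 10.** Imposing 5 of 10 on the printed limits gives 0.363–0.396 at 30% and 0.855–0.864 at 40%, so it recovers neither 0.3 nor 0.3980. To see how often it matters, take the 252 orderings of 5 events in 10 patients. The printed limits have already halted 106 to 181 of them by n = 9, leaving 71 to 146.

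- At 30%, each ordering has probability 0.3^5 × 0.7^5 = 0.000408: 71 × 0.000408 = 0.029 and 146 × 0.000408 = 0.060.
- At 40%, each has 0.4^5 × 0.6^5 = 0.000796: 71 × 0.000796 = 0.057 and 146 × 0.000796 = 0.116.

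**Step 4. Sensitivity to the first row**

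- Drop that row, keeping only 3 of 3 and 4 of 6 from the narrative with the complete rows from n = 23: 0.313 at 30%.
- Let the missing cell be b_3 = 2, against the narrative: 0.443 at 30%, with expected patients still 3.07 at 90% and 3.00 at 100%.
- Stop counting at 47 patients, if full follow-up were read that narrowly: 0.301–0.353 at 30%.

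None of these is at or below 0.3.

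**The case against.** The best defence is that the rule is clear in practice. The text ties halting to b_n in the table, the worked examples are introduced as consequences of that algorithm, and the operating-characteristics table triggers no action. On that reading the printed limits govern and the rest is faulty illustration. This is a reasonable reading, and it narrows the operational risk to the examples. It does not make the 0.3 promise true of the printed limits, and the protocol does not say which statement prevails.

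Three narrower objections also carry weight.

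- The upper figures at n = 10 (0.060 and 0.116) arise where the printed limit at n = 9 is 6. Of the 146 orderings left there, 47 already have 5 events by n = 9, so the narrative's 5-of-9 example would have halted them one patient earlier. Counting only disagreements that begin at n = 10 leaves 71 to 99 orderings: 99 × 0.000408 = 0.040 at 30% and 99 × 0.000796 = 0.079 at 40%.
- The 0.340–0.388 range assumes one lost cell and that the rest of a damaged row was read correctly. It is therefore secondary to the conflict between text and table, which needs no such assumption.
- The figure of 47 belongs to local-control evaluability (Sections 11.2 and 11.4), not toxicity, so that sensitivity is only a bound.

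The consequence is also limited. The printed limits halt more readily than the text promises, so participants are not less protected than that statement implies, and the largest table mismatches lie at rates far above the 5–25% that Section 11.2 quotes from earlier studies.

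**Conclusion.** The concern holds. Two contradictions can be read from the page without calculation: at most 0.3 against 0.3980, and 2.00 expected patients under a rule that first looks at three. A third, 5 of 10 against a limit of 6, holds under every in-order placement of the missing cell.

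By recomputation, the printed limits have a false-stop probability of 0.340–0.388 at a 30% rate. That is 0.04 to 0.09 above the promise and 0.01 to 0.06 below the table. It rests on stopping at b_n or more, a first look at n = 3, b_3 = 3, all 67 patients counted, and a single missing cell.

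The direction is mixed: the printed limits stop more often than the text promises and less often than the table or the 5-of-10 example implies. The rule keeps a stopping probability of at least 0.848 at 40%, and no primary estimate or sample size depends on it. This should be corrected, but it is not a fatal flaw.

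**What to change.** Generate one boundary with the plan's own settings (first look at n = 3, maximum 67) and print every limit. Take the operating-characteristics table and all worked examples from that same boundary, including those at n = 9 and n = 10. Then either make the boundary meet the stated 0.3 or replace that figure with the probability it delivers. The text and table limits at n = 10 must be reconciled; which limits apply is the sponsor's decision.

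The cost is a short recomputation and a wording change, with no extra patients. Keeping the printed limits means stating a less favourable false-stop figure, about 0.34 to 0.39. Keeping 0.3 costs some stopping probability at a 40% rate. As an illustration only, and not a plan figure, a constant-level boundary from n = 3 that gives 0.299 at 30% stops with probability 0.805 at 40%, against 0.848–0.862 for the printed limits.
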